### 11.4.2. Treatment Emergent Flag for Adverse Events

Flag	Definition
Treatment Emergent	
 
• If AE onset date is on or after treatment start date & on or before treatment stop date.
 
• Study Treatment Start Date <math>\leq</math> AE Start Date <math>\leq</math> Study Treatment Stop Date
 
• For Part 1: AE onset is during one period and worsens during a later period it would be counted in both periods. For the initial period, the logic would be as above. For the later period the logic would use the treatment dates associated with the later period
 
• Treatment Period Start Date <math>\leq</math> AE Worsening Date <math>\leq</math> Study Treatment Stop Date
 

**NOTES:**

- If the study treatment stop date is missing, then the AE will be considered to be On-Treatment.
- Time of study treatment dosing and start/stop time of AEs should be considered, if collected.

### 11.4.3. Adverse Events Assignment to Treatment Period for Part 1

Adverse events (AEs) will be assigned to a treatment period and corresponding treatment received in that treatment period after the imputations defined in RAP section 12.7.2 have been performed.

- Treatment Period 1: all AEs with start date/time at the time of or after administration in Treatment Period 1 and before administration in Treatment Period 2
- Treatment Period 2: all AEs with start date/time at the time of or after administration in Treatment Period 2 and before administration in Treatment Period 3
- Treatment Period 3: all AEs with start date/time at the time of or after administration in Treatment Period 3 and before administration in Treatment Period 4
- Treatment Period 4: all AEs with start date/time at the time of or after administration in Treatment Period 4

Thus, AEs occurring during the 1st washout will be assigned to the treatment received in Treatment Period 1, AEs occurring during the 2th washout will be assigned to the treatment received in Treatment Period 2, AEs occurring during the 3rd washout will be assigned to the treatment received in Treatment Period 3 and AEs occurring during final follow-up will be assigned to the treatment received in Treatment Period 4.

### 11.4.4. Concomitant Medication Assignment to Treatment Period for Part 1

Concomitant medications (CMs) will be assigned to a treatment period and corresponding treatment received in that treatment period after the imputations defined in RAP section 12.7.2 have been performed.

- Treatment Period 1: all CMs with start date/time at the time of or after administration in Treatment Period 1 and before administration in Treatment Period 2
- Treatment Period 2: all CMs with start date/time at the time of or after administration in Treatment Period 2 and before administration in Treatment Period 3
- Treatment Period 3: all CMs with start date/time at the time of or after administration in Treatment Period 3 and before administration in Treatment Period 4
- Treatment Period 4: all CMs with start date/time at the time of or after administration in Treatment Period 4

Thus, CMs occurring during the 1st washout will be assigned to the treatment received in Treatment Period 1, CMs occurring during the 2th washout will be assigned to the treatment received in Treatment Period 2, CMs occurring during the 3rd washout will be assigned to the treatment received in Treatment Period 3, and CMs occurring during follow-up will be assigned to the treatment received in Treatment Period 4.

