Sequence 3	Dose 1	Dose 3	Placebo	Dose 7
Sequence 4	Dose 1	Dose 3	Dose 5	Placebo

Cohort 2	Period 1	Period 2	Period 3	Period 4
Sequence 1	Placebo	Dose 4	Dose 6	Dose 8
Sequence 2	Dose 2	Placebo	Dose 6	Dose 8
Sequence 3	Dose 2	Dose 4	Placebo	Dose 8
Sequence 4	Dose 2	Dose 4	Dose 6	Placebo

Part 1 SAD: Sentinel Dosing

To conservatively assess safety, at the start of each dose period of the SAD, 2 out of the 8 participants will serve as sentinel participants with one receiving GSK3640254 and the other receiving placebo. These sentinel participants will be followed clinically for 24 hours after dose administration to monitor for emergence of adverse events. If there are no safety concerns, in the judgment of the PI, on review of the 24-hour safety data (e.g. vital signs, ECGs, and adverse events) for the sentinel participants, the remaining 6 participants will subsequently be administered either GSK3640254 or PBO according to randomization schedules.

Part 1 SAD: Dose Escalation

Dose escalation in Part 1 will be determined by the VH/GSK study team and the PI based on the double-blind (sponsor-unblinded) safety data and the PK data from the current and

previous dose(s). Dose escalation will not exceed approximately 3-fold between doses up to approximately the predicted minimally effective dose and will not exceed 2-fold thereafter. Dose escalation in Part 1 will require (from the current dosing group) at least 24 hours of safety and PK data from 4 participants receiving active drug. Dose escalation will be guided by safety as well as the SAD PK stopping criteria (see Section 8). Due to the alternating dosing periods between Cohort 1 and Cohort 2, a participant in either cohort will receive the next dose after approximately 3 or 4 weeks.

Part 2 (MAD):

Part 2 consists of four ascending repeat-dose cohorts (Cohorts 3 to 6), each with 8 participants (active/PBO=6/2) who will receive a once-daily dose of GSK3640254 or PBO for 14 days. Details of the starting dose and dose escalations in Part 2 (MAD) are provided in Section 5.5.4.

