Part 2 also includes an Expansion Cohort which was conducted at the conclusion of Cohort 5. VH's prior and structurally similar MI (GSK3532795) ceased development in Phase 2b (due in part to a higher proportion of participants experiencing GI intolerability). GSK3532795, studied in Phase 1 studies of normal healthy volunteers showed diarrhoea of up to 65%. The Expansion Cohort will evaluate the rate of GI intolerability in 24 participants (active/PBO =18/6). The dose studied (200 mg) was previously studied doses in the MAD and did not meet safety or PK stopping criteria. While no formal statistical testing will be performed, a summary of GI AEs will be provided from: 1) 24 participants receiving one of the GSK3640254 doses studied

previously and 2) 14 participants receiving placebo across the entire MAD. These numbers of participants should provide sufficient clinical inference and better estimation of GI AEs frequency at a given dose (which can be used to inform subsequent dose selection/therapeutic index for HIV-1 infected participants).

Participants in both Part 1 and Part 2 will have a screening visit within 30 days prior to first dose and a follow-up visit 7-14 days after the last dose. Maximum duration of study participation will be approximately 12 weeks.

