9.2.1. Time Period and Frequency for Collecting AE and SAE Information

- All SAEs will be collected from the signing of the ICF until the follow-up visit at the time points specified in the [SoA](#) (Section 2).
- All AEs will be collected from the start of treatment until the follow-up visit at the time points specified in the [SoA](#) (Section 2).
- Medical occurrences that begin before the start of study treatment but after obtaining informed consent will be recorded on the Medical History/Current Medical Conditions section of the case report form (CRF) not the AE section.
- All SAEs will be recorded and reported to the sponsor or designee within 24 hours, as indicated in [Appendix 4](#). The investigator will submit any updated SAE data to the sponsor within 24 hours of it being available.
- Investigators are not obligated to actively seek AEs or SAEs in former study participants. However, if the investigator learns of any SAE, including a death, at any time after a participant has been discharged from the study, and he/she considers the event to be reasonably related to the study treatment or study participation, the investigator must promptly notify the sponsor.
- The method of recording, evaluating, and assessing causality of AEs and SAEs and the procedures for completing and transmitting SAE reports are provided in [Appendix 4](#).

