## 2.3. Study Design

Overview of Study Design and Key Features	

The diagram illustrates the study design. Part 1 (SAD) consists of two cohorts, Cohort 1 and Cohort 2, each with four periods of treatment. Cohort 1 doses are 1 mg, 10 mg, 100 mg, and 400 mg. Cohort 2 doses are 3 mg, 30 mg, 200 mg, and 700 mg. Part 2 (MAD) consists of five cohorts: Cohort 3 (50 mg QD), Cohort 4 (100 mg QD), Cohort 5 (200 mg QD), Cohort 6 (320 mg QD), and an Expansion Cohort (200 mg QD). All cohorts in Part 2 have 14 days of treatment and n=8 participants (A/P=6/2), except for the Expansion Cohort which has n=24 (A/P=18/6).
	
Design Features	
 
Two part, Phase 1, double-blind (sponsor-unblinded), randomized, placebo controlled, single- and repeat-dose escalation study.
 
 
Part 1 (SAD):
 
 
SAD portion will be conducted in an interlocking fashion with 2 separate cohorts of 8 healthy participants each. Each of these 2 cohorts will contain up to 4 escalating doses of GSK3640254.
 
In each escalating period and Cohort, 6 participants will be randomized to GSK3640254 and 2 participants will be randomized to placebo.
 
Participants in Cohort 1 and Cohort 2 will follow the same randomization strategy with alternating ascending doses with 4-period crossover, placebo-controlled.
 
 
Part 2 (MAD):
 
 
Part 2 consists of 4 ascending repeat-dose cohorts (Cohorts 3 to 6), each with 8 participants (active/PBO=6/2) who will receive a once-daily dose of GSK3640254 or PBO for 14 days.
 
Part 2 also includes an Expansion Cohort which will be conducted at the conclusion of cohort 5.
 
The Expansion Cohort will evaluate the rate of GI intolerability in 24 participants (active/PBO =18/6).
 

Dosing	
Part 1 (SAD):
 
 
The dose for Part 1 Cohort 1 of this study were 1 mg for Period 1, 10 mg for Period 2, 100 mg for Period 3 and 400 mg for Period 4.
 
The dose for Part 1 Cohort 2 of this study will be 3 mg for Period 1, 30 mg for Period 2, 200 mg for Period 3 and 700 mg for Period 4.
 
 
Part 2 (MAD):
 
 
The dose for Part 2 of this study were 50 mg for Cohort 3, 100 mg for Cohort 4, 200 mg for Cohort 5 and the expansion cohort, and 320 mg for cohort 6.
 

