**NOTES:**

- Order represents treatments being presented in TFL, as appropriate.
- Placebo is pooled by part

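### Part 1 AE tables count about 3–4 weeks after dosing in Periods 1–3 but only 7–14 days in Period 4, which can understate late-onset and background AEs at 400 and 700 mg

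*SAP*

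**What the plan says.** **Assignment.** SAP Section 11.4.3 gives Period 3 "all AEs with start date/time at the time of or after administration in Treatment Period 3 and before administration in Treatment Period 4". Periods 1 and 2 follow the same pattern, and washout events are explicitly attached to the preceding treatment. Period 4 has no stated end; the section adds that "AEs occurring during final follow-up will be assigned to the treatment received in Treatment Period 4".

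**Timing.** Protocol Section 5.1 says that in Part 1 "a participant in either cohort will receive the next dose after approximately 3 or 4 weeks", and that participants have "a follow-up visit 7-14 days after the last dose". Protocol Section 9.2.1 closes collection: "All AEs will be collected from the start of treatment until the follow-up visit at the time points specified in the" Schedule of Activities.

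**Dose and period.** SAP Section 2.3 lists "100 mg for Period 3 and 400 mg for Period 4" for Cohort 1 and "200 mg for Period 3 and 700 mg for Period 4" for Cohort 2. Neither top dose appears in any other period.

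**Placebo.** Protocol Table 5 puts two participants on each of four sequences per cohort, each with one placebo period. SAP Section 5.1 notes: "Placebo is pooled by part".

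**Displays.** SAP Section 7.2.1 summarises the whole of the AE data by treatment group. The programming note to Table 3.1 takes the number of subjects on each treatment as denominator. No AE table mentions person-time or a common window.

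**Other windows.** Section 11.4.1 defines an on-treatment phase ending 5 days after the last treatment stop date. Section 11.4.2 defines a treatment-emergent flag that ends at the treatment stop date. No AE display is said to use either.

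**The concern.** Safety and tolerability by dose is the primary objective, and the by-treatment AE tables are its main output. In Part 1 the time over which an AE can be counted depends on the period, and the period is tied to the dose. The two highest doses always have the short window; every lower dose has the long one, and so do most placebo exposures.

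Background events build up with time. The blinded SAD table in Protocol Section 3.2.2 includes nasopharyngitis, viral infection, contusion, skin abrasion and limb injury. Participants leave the unit at 96 h, so the extra days in Periods 1–3 are mostly spent at home. With no drug effect at all, fewer participants would be expected to have an AE at 400 and 700 mg than at lower doses or on placebo. A real increase in late events at those doses could be partly masked.

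**Working it through.** **1. Windows.** W is the Periods 1–3 window, equal to the dosing interval: 21–28 days, midpoint 24.5. F is the Period 4 window, dosing to follow-up visit: 7–14 days, midpoint 10.5.

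**2. Placebo.** 2 participants × 4 sequences × 2 cohorts = 16 planned exposures, 4 per period. So 12/16 = 75% have window W and 25% have window F, and the mean placebo window is 0.75W + 0.25F.

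| W (days) | F (days) | F/W | Mean placebo window (days) | F / placebo window |
|---|---|---|---|---|
| 21 | 7 | 0.33 | 17.5 | 0.40 |
| 21 | 14 | 0.67 | 19.25 | 0.73 |
| 24.5 | 10.5 | 0.43 | 21.0 | 0.50 |
| 28 | 7 | 0.25 | 22.75 | 0.31 |
| 28 | 14 | 0.50 | 24.5 | 0.57 |

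The 3–4 week interval is approximate. Three intervals plus follow-up take (3 × 21 + 7)/7 = 10 to (3 × 28 + 14)/7 = 14 weeks from first dose. The stated maximum participation of approximately 12 weeks therefore favours the shorter intervals. Even at 21 days the ratio is only 0.33–0.67.

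**3. Illustration with no drug effect.** The documents give no background AE rate, so a constant hazard h of first events per day is assumed. The chance of at least one event in t days is 1 − exp(−ht). Pooled placebo is 0.75 × the first column + 0.25 × the second.

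| h (assumed) | Periods 1–3, 24.5 days | Period 4, 10.5 days | Pooled placebo | Common 7 days, any column |
|---|---|---|---|---|
| 0.01 | 22% | 10% | 19% | 7% |
| 0.02 | 39% | 19% | 34% | 13% |
| 0.03 | 52% | 27% | 46% | 19% |

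With 6 active participants per dose, h = 0.02 gives 6 × 0.39 = 2.3 against 6 × 0.19 = 1.1 participants with an event.

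**4. Blinded counts so far.** Protocol Table 1 totals 9, 4, 13, 6, 10 and 6 events in the six Periods 1–3 columns, which is 48 over 6 × 8 = 48 planned participant-periods, or 1.00 each. The 400 and 700 mg columns total 7 + 5 = 12 over 16, or 0.75 each. The rate ratio is 0.75. A rough Poisson 95% interval is 0.75 × exp(±1.96 × √(1/12 + 1/48)) = 0.40 to 1.41, which contains both 0.43 and 1. These are preliminary event counts with active and placebo mixed.

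**5. The other rules.** With period-specific dates, the 11.4.2 flag gives every single dose the same one-day window. With the overall last stop date, it leaves Periods 1–3 unchanged and cuts Period 4 to one day. The 11.4.1 phase cuts Period 4 to 5 days, a ratio of 5/24.5 = 0.20.

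**The case against.** **Section 11.4.3 may only say which treatment an AE belongs to.** It does not exclude a treatment-emergent filter, and 11.4.2 has logic specific to Part 1. With period-specific dates that filter would remove the imbalance. A reader might infer from the table titles that the filter is ruled out, but only Tables 3.2 and 3.3 have the word All in the title, and there it may only mark scope. The better support is Section 7.2.1, together with the fact that no AE display invokes the flag or the phase. What stands is that the SAP never names the governing window, and its candidate windows conflict.

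**Close observation is the same in every period.** The in-unit stay runs from Day −2 to 96 h throughout. Section 11.4.1 also assigns follow-up from Periods 1–3 to the same period. Both are true, but 11.4.3 still adds the washout up to the next dose.

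**Acute effects are not lost.** Mean half-life is about 24 h (Protocol Section 3.2.2), so 7 days covers about 7 half-lives. Table 3.3 should leave out most colds and bruises, since it is limited to drug-related events. The four Period 4 placebo exposures share the short window. All of this stands and limits the point to late and background events, although pooling hides the same-period placebo comparison.

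**Crediting washout events to the preceding dose is a cautious choice in a first-in-human study.** Replacing the tables with a 7-day cut-off would drop late events, including Days 8–14 at 400 and 700 mg. This stands, and it is why the common window should be added rather than substituted.

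**Conclusion.** The point holds for Part 1 AE percentages in Tables 3.1–3.3 and 3.5–3.8. As the plan reads, 400 and 700 mg have about 0.43 of the window of the lower doses and 0.50 of the mean pooled placebo window at the midpoints. The ranges are 0.25–0.67 and 0.31–0.73. These ratios rest on three readings: 11.4.3 governs the tables, Period 4 ends at the follow-up visit, and the planned placebo allocation is kept.

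A reader might go further and infer that the tables are biased towards showing no dose relationship exactly where one would appear. The documents do not support that. Early drug effects are counted alike in all periods, the percentages in the illustration depend on an assumed hazard, and the blinded counts neither show nor exclude the predicted gap. The analyses are also descriptive (SAP Section 2.4), and with six active participants per dose the illustrated gap is about one participant. The supported conclusion is that late-onset and background AEs can be understated at the two highest doses, by an amount that cannot be fixed from the documents.

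**What to change.** In the SAP:

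1. State in Sections 7.2.1 and 11.4.3 that the 11.4.3 assignment governs the existing Part 1 AE tables and listings. Say what use, if any, is made of the 11.4.1 phase and the 11.4.2 flag. Leave the existing tables in place.
2. Add for Part 1 a by-treatment AE summary restricted to one window, from dosing to 7 days after dosing, in every period and for placebo. It should cover at least the overview, all-AE and special-interest tables (3.1, 3.2 and 3.5). Seven days is the shortest follow-up the protocol schedules after the last dose, so the window ratio becomes 1.0 for every column. The alternative is to show AE rates per person-day beside the percentages.
3. Footnote the Part 1 AE tables with the window length by period.

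The cost is one derived flag, a few extra displays and SAP wording, with no new data. The common-window summary leaves out late AEs, but these stay in the existing tables and listings.

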## 11.5. Appendix 5: Data Display Standards & Handling Conventions

### 11.5.1. Reporting Process

Software	

 
The currently supported versions of SAS software will be used.
 
	
Reporting Area	
HARP Server	: US1SALX00259
HARP Compound	: 3640254
Analysis Datasets	

 
Analysis datasets will be created according to CDISC standards (SDTM IG Version 3.13 & ADaM IG Version 1.0]. If the Study Data Standardization Plan (SDSP) exists for a study, ensure the CDISC versions are consistent.
 
	
Generation of RTF Files	

 
RTF files will be generated for SAC.
 
	

### 11.5.2. Reporting Standards

General

 
The current GSK Integrated Data Standards Library (IDSL) will be applied for reporting, unless otherwise stated (IDSL Standards Location: https://spope.gsk.com/sites/IDSLLibrary/SitePages/Home.aspx): 
 
4.03 to 4.23: General Principles
 
5.01 to 5.08: Principles Related to Data Listings
 
6.01 to 6.11: Principles Related to Summary Tables
 
7.01 to 7.13: Principles Related to Graphics
 
 
 
Do not include subject level listings in the main body of the GSK Clinical Study Report. All subject level listings should be located in the modular appendices as ICH or non-ICH listings
 
Statistical analyses of the pharmacokinetic parameter data will be the responsibility of Clinical Statistics, GSK.
 

Formats

 
GSK IDSL Statistical Principles (5.03 & 6.06.3) for decimal places (DP's) will be adopted for reporting of data based on the raw data collected, unless otherwise stated.
 
Numeric data will be reported at the precision collected on the eCRF.
 
The reported precision from non eCRF sources will follow the IDSL statistical principles but may be adjusted to a clinically interpretable number of DP's.
 

Planned and Actual Time

 
Reporting for tables, figures and formal statistical analyses: 
 
Planned time relative to dosing will be used in figures, summaries, statistical analyses and calculation of any derived parameters, unless otherwise stated.
 
The impact of any major deviation from the planned assessment times and/or scheduled visit days on the analyses and interpretation of the results will be assessed as appropriate.
 
 
 
Reporting for Data Listings: 
 
Planned and actual time relative to study drug dosing will be shown in listings (Refer to IDSL Statistical Principle 5.05.1).
 
Unscheduled or unplanned readings will be presented within the subject's listings.
 
 
 

Unscheduled Visits

 
• Unscheduled visits will not be included in summary tables and/or figures.
 
• All unscheduled visits will be included in listings.
 
	
Descriptive Summary Statistics	
Continuous Data	Refer to IDSL Statistical Principle 6.06.1
Categorical Data	N, n, frequency, %
Graphical Displays	

 
• Refer to IDSL Statistical Principals 7.01 to 7.13.
 
	
Plasma GSK3640254 concentrations and PK data	

 
• Will be summarized by treatment and listed by participant. Unless stated otherwise, descriptive summaries will include number (n), mean, standard deviation (SD), coefficient of variation (%CV), median, minimum, and maximum for continuous variables, n and percent (%) for categorical variables, and geometric mean, 95% confidence interval (CI), and the between-participant CV (%CVb) for the log-transformed PK parameters.
 
	
Between-subject coefficient of variation (%CVb)	

 
• Untransformed Data: <math>100 * (SD/Mean)</math>
 
• Transformed Data: <math>100 * (\sqrt{\exp(SD_{\log}^2)-1})</math>, where <math>SD_{\log}</math> indicates the standard deviation of log-transformed data.
 
• Within subject coefficient of variation (%CVw) will be calculated according to the following method:  <math>CVw(\%) = \sqrt{\exp(MSE) - 1} \times 100</math> and MSE is the residual mean squared error from the model.            CVw represents a pooled measure of within-subject variability across the treatments.
 
	

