		50 mg	100 mg	200 mg
Ear and Labyrinth Disorders	Ear Discomfort			1
	Excessive Cerumen Production			1
Renal and Urinary Disorders	Pollakiuria			1
	Dysuria			1
Respiratory, Thoracic, and Mediastinal Disorders	Epistaxis	1		
	Transaminases Increased	1		
Cardiac Disorders	Palpitations			1
Total AEs by Blinded MAD Cohort/Period		19	17	43

Preliminary PK parameters for GSK3640254 following single dose administration from 1 to 700 mg are summarized in [Table 3](#). GSK3640254 is slowly absorbed with maximum concentration observed on average 3-4 hours after dosing and slowly eliminated with an average half-life of 24 hours. C_{max} and AUC increased in a close to dose proportional manner from 1 to 400 mg with a plateauing in exposure at the 700 mg dose. The maximum observed mean C_{max} for the single dose administration ([Table 3](#)) is 1881 ng/mL at the dose of 400 mg. The maximum observed mean AUC(0-inf) for the single dose administration ([Table 3](#)) is 43116 ng.hr/mL at the dose of 400 mg. The mean exposure observed at 700 mg is slightly lower than that at 400 mg single administration and thus we anticipate similar exposures with doses greater than 700 mg.

Table 3 Summary of Preliminary PK Parameters Following Single Doses of GSK3640254 in study 207187

PK Parameter	Dose							
	1 mg	3 mg	10 mg	30 mg	100 mg	200 mg	400 mg	700 mg
	Geometric Mean (CV%) [N]*							
Cmax	4.9 (16) [6]	13.8 (31) [6]	47 (30) [6]	129.8 (21) [6]	372.1 (72) [6]	578.9 (27) [6]	1881 (50) [6]	1760.8 (44) [6]
Tmax	3.5 (2.5-6) [6]	4.5 (2-5) [6]	3.5 (2.5-5) [6]	4 (2.5-5) [6]	3.8 (2-5) [6]	3 (2-4) [6]	3.3 (2-6) [6]	3.3 (2-4.5) [6]
T1/2(z)	NC	22 (14) [6]	25.8 (17) [6]	23.3 (16) [6]	23.9 (14) [6]	23.2 (17) [6]	23.3 (16) [6]	22.2 (28) [6]
AUC	NC	340 (29) [6]	1229.3 (19) [6]	3008 (26) [6]	8566.4 (67) [6]	14978 (41) [6]	43115.7 (52) [6]	39972.5 (50) [6]
* Tmax has been reported as Median (Min - Max)								
AUC represents AUC(0-inf); NC: Not Computed								
Units: Cmax in ng/mL, AUC in ng.h/mL, t1/2 and tmax in hours								

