10. STATISTICAL CONSIDERATIONS

10.1. Sample Size Determination

No formal statistical hypotheses are to be tested. Sample size is based on feasibility. No formal calculation of power or sample size for Parts 1 and 2 of the study has been performed. A sample size of approximately 8 participants per dose-cohort should be sufficient to provide useful estimates of both inter- and intra-participant variability for GSK3640254 PK parameters, and initial safety assessment.

As described in Section 5.1, an expansion cohort is included in this study in order to evaluate the rate of GI intolerability. No formal statistical testing will be performed. However, based on prior information from GSK3532795 studies, a conservative clinical estimate of GI AEs in those receiving placebo would be 10%; a sample size of 24 participants on active and 14 participants on placebo would have 90% power to detect a 45% difference between placebo and GSK3640254.

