### 8.1.4.1. Statistical Methodology Specification

#### Dose Proportionality-Power model:

*Part 1, and 2:*

Dose proportionality of GSK3640254 following single-dose administration in Part 1 and following single-dose and repeat-dose administration in Part 2 of the study will be assessed separately using the power model (Smith, 2000) as described below:

$$y = \alpha * dose^{\beta}$$

where y denotes the PK parameter being analyzed [for Part 1: AUC(0-∞), AUC(0-24), and Cmax. For Part 2: AUC(0-24), Cmax on Day1;

AUC(0-τ), Cmax, Cτ on Day 14] . Dose proportionality implies that β=1 and will be assessed by estimating β along with its confidence interval. The exponent, β, in the power model will be estimated by regressing the loge-transformed PK parameter on loge dose.

$$\log(y) = \log(\alpha) + \beta * \log(\text{dose})$$

The power model will be fitted by restricted maximum likelihood (REML) using SAS

Proc Mixed. For Part 1, a power model with subject as the random effect will be fitted. If the model does not converge then a fixed effect power model will be fitted. For Part 2, a fixed effect power model will be fitted. The mean slope will be estimated from the power model and the corresponding 90% confidence interval calculated. Intra-subject CV% calculated from the model will be presented in the table. Point estimates and confidence intervals for the slope will be reported to 4 decimal places with no rounding.

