#### **Part 1,**

*An example of SAS code is included here for the power model approach.*

*ODS output solutionf=stat*

*Proc Mixed;*

*class subject;*

*model logPKvar = logdose /cl alpha=0.1 solution ddfm=kr;*

*random intercept /subject=subject type=un;*

*run;*

*If the above model still does not converge, then use:*

*ODS output solutionf=stat*

*Proc Mixed;*

*model logPKvar = logdose /cl alpha=0.1 solution ddfm=kr;*

*run;*

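### The Part 1 intra-subject CV is taken from the residual of a one-slope power model, so it will be modestly overstated if the dose means do not lie on a single log-log line.

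*SAP*

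**What the plan says.** SAP 11.5.2 (Reporting Standards) sets CVw = 100·√(exp(MSE) − 1), where "MSE is the residual mean squared error from the model". It adds that "CVw represents a pooled measure of within-subject variability across the treatments". It does not say which model is meant.

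The power-model paragraph of SAP 8.1.4.1 supplies the model: "Intra-subject CV% calculated from the model will be presented in the table". On structure it says "For Part 1, a power model with subject as the random effect will be fitted". The Part 1 example code has a single continuous dose term, "model logPKvar = logdose /cl alpha=0.1 solution ddfm=kr", plus a random intercept per subject. It has no dose-class or lack-of-fit term. The fallback drops the subject term: "If the model does not converge then a fixed effect power model will be fitted".

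Protocol 10.1 gives as one purpose of the sample size "useful estimates of both inter- and intra-participant variability for GSK3640254 PK parameters". Protocol 3.2.2 describes exposure as close to proportional from 1 to 400 mg, "with a plateauing in exposure at the 700 mg dose".

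**The concern.** The residual of a straight-line model estimates within-subject variance only if the dose means lie on the line. In Part 1 each participant takes three different active doses, so a departure of some dose means from the line shows up partly as variation within participants. The SAP would print that under a within-subject label, although non-proportionality is a separate secondary objective. The protocol's own description gives a reason to doubt a single line over 1 to 700 mg. What is at stake is the accuracy of one descriptive figure that Protocol 10.1 names as a purpose of the design.

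**Working it through.** The documents state no CVw value, so there is no planned figure to reproduce. Individual data are not available either.

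**Inputs.** Protocol Table 3 gives geometric means and CVs, n = 6 per dose, for 1 to 700 mg (AUC(0-inf) not computed at 1 mg). Protocol Table 5 gives the sequences: 16 participants, two cohorts with different doses, three active doses each, 48 active observations. The split of variance within and between participants is not stated. It is varied below.

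**Step 1: how far the preliminary means lie from one line.** Log geometric mean regressed on log dose:
- Cmax: slope 0.926. Log-scale deviations are −0.19 at 200 mg (−17%), +0.35 at 400 mg (+42%) and −0.24 at 700 mg (−21%). The other doses are within 8%.
- AUC(0-inf): slope 0.902, with −9%, +40% and −22% (rounded) at the same doses.

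**Step 2: is the lack of fit established?** Pooled within-dose log variance is the mean of ln(1 + CV²): 0.142 for Cmax and 0.167 for AUC. The lack-of-fit mean square is 6·Σ(deviation²)/(k − 2), with k the number of doses.
- Cmax: 6 × 0.2277/6 = 0.228, so F = 0.228/0.142 = 1.6, p = 0.17.
- AUC: 6 × 0.2028/5 = 0.243, so F = 0.243/0.167 = 1.5, p = 0.23.
- Each Cmax mean has a standard error of about √(0.142/6) = 0.15, so the three deviations are about 1.2, 2.3 and 1.5 standard errors.
- The denominator contains between-participant variance. If only 0.1 to 0.2 of it is within-participant, the approximate p for Cmax is 0.01 to 0.02.

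**Step 3: data matched to Table 3.** Data were simulated on the planned design and forced to the Table 3 means and CVs, then fitted by REML with the SAP model and with dose as a class effect plus random subject.

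| Within-subject share | Cmax: SAP model / dose class | AUC: SAP model / dose class |
|---|---|---|
| 0.2 | 28.6% / 23.9% | 28.6% / 24.9% |
| 0.5 | 33.0% / 30.4% | 34.4% / 32.7% |
| 0.8 | 37.0% / 35.3% | 39.1% / 38.5% |

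Over shares 0.1 to 1.0 the median excess is 1.6 to 5.6 points for Cmax and 0.5 to 4.7 for AUC. It is largest at small shares. In single data sets with a high share it can be about zero.

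**Step 4: assumed true means.** Between-participant CV assumed 30%, true CVw 15/25/35%:
- Table 3 Cmax means exactly true: the SAP model gives about 22/31/39%. For AUC it gives 21/29/38%.
- Proportional to 400 mg, then flat to 700 mg: about 24/31/40%.
- Exactly proportional: 15/25/34%, no bias.
- Dose as a class effect: within about one point of the true value in every case.

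A milder reading keeps the line fitted to 1–400 mg (slope 0.952) and lets only 700 mg fall below it. Cmax CVw is then 20.6/29.5/36.9% against a true 17.0/27.1/34.7%, an excess of 2.2 to 3.6 points.

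**Step 5: where the lack of fit goes.** If all of the Cmax lack of fit fell on the residual's 31 degrees of freedom, it would add 6 × 0.2277/31 = 0.044 to the variance. In the Table 3 scenario the addition is smaller. At a true 25%, for example, it is ln(1 + 0.31²) − ln(1 + 0.25²) = 0.092 − 0.061 = 0.031. The two cohorts receive different doses, so some goes into the subject variance instead.

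**Step 6: degrees of freedom.** SAP model: 48 − 16 − 1 = 31. Dose as class: 48 − 16 − 6 = 26 (three dose contrasts within each cohort).

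**The case against.** The strongest reply is that the bias is conditional and small. Step 2 does not establish curvature, and treating the Table 3 means as true mistakes sample means for parameters. Even an unbiased estimate with 26 to 31 degrees of freedom at a true 25% has a 95% interval of about 20 to 35%, so the likely excess lies within sampling error. The figure is descriptive, no hypothesis is tested, and dose escalation uses a separate Bayesian model. All of this stands and limits the weight of the point. It does not favour the power-model residual, because the dose-class fit is approximately unbiased whether or not the line holds.

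SAP 8.1.4.1 also allows a dose-class ANOVA if the power model does not show proportionality. That does not supply the figure: it is optional, and its example code has no subject term.

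Three stronger readings are tempting and are not supported:
- *Every participant receives doses both on and off the line.* Cohort 1, Sequence 4 receives 1, 10 and 100 mg, all close to the fitted line. Under the described plateau, no Cohort 1 participant receives the off-line dose.
- *This is the only planned model with repeated data per participant.* The accumulation and steady-state models also carry a random subject term. They are run by dose, so they cannot give a CV pooled across treatments.
- *A later crossover would be oversized by 40 to 50%.* That uses ln(1 + 0.30²)/ln(1 + 0.25²) = 1.42, or 1.51 at 31%, from the larger-bias scenarios at one true value. The data-matched Cmax pairs give 1.17 (33.0% against 30.4%) and 1.09 (37.0% against 35.3%). About 1.4 appears only at a low within-subject share. The documents foresee a later food-effect study but do not say that this CV will size it.

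**Conclusion.** The point holds in conditional form. Read together, SAP 8.1.4.1 and 11.5.2 label as within-subject variability a residual that also absorbs part of any departure from a single log-log line. A reader might infer that the reported CV is certain to be too high. The documents do not support that, because the overstatement requires the true dose means to leave the line, which the described plateau suggests and n = 6 per dose leaves open.

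On data matched to Table 3 the median excess is about 1.6 to 5.6 CV points for Cmax and 0.5 to 4.7 for AUC(0-inf). It is about 4 to 9 points for Cmax (3 to 6 for AUC) if the Table 3 means are exactly true or, for Cmax, the described plateau is, with true CVw of 15 to 35% and between-participant CV of 30%. It is nil under proportionality. These sizes rest on an assumed within-subject share and cannot be fixed without individual data. The slope estimate and the proportionality conclusion are unaffected. It is a modest correction, worth making because it is cheap.

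**What to change.** Keep the power model for the slope and its 90% interval. Take the Part 1 CVw from

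`class subject treatment; model logPKvar = treatment / ddfm=kr; random subject;`

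and report 100·√(exp(residual variance) − 1) from that fit. The simplest route is to add the subject term to the Part 1 dose-class fit already sketched in SAP 8.1.4.1 and run it unconditionally. Dose normalisation there shifts only the dose means, so the residual is the same. Name this model in the power-model paragraph of 8.1.4.1 and in 11.5.2. If the fallback without a subject term is used for the slope, do not report its residual (CV about 41% for Cmax from Table 3) as intra-subject.

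The cost is one further PROC MIXED call per parameter, a sentence in each of the two sections, and 26 instead of 31 within-subject degrees of freedom. At a true 25%, the 95% interval goes from about 20–34% to about 20–35%.
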